## 2 FLOW CHARTS

### 2.1 GRAPHICAL STUDY DESIGN

Estimated timelines

### 2.2 STUDY FLOW CHART

The study consists of the documentation of an e-CRF for adult patients with CAD (please refer to Section 10.1 for details).

Note: The observational study operates under real clinical practice conditions; it collects only available data and necessary data for the purpose. There are no imposed protocol visits or procedures.

Protocol template for disease observational studies			
		Research and Development	
QSD-003149	Disease observational study with disease Application Date (DD/MM/YYYY) : dd-Mmm-09/11/2020	protoco v. 6.0/yyyy	EFFECTIVE

<DD-MM-YYYY HH:mm:ss> < 15-01-2021 21:03:21 > UTC

primary data collection

Study Number: GER-CAD-19-11180

Version number: ~~V6~~V7.0

Study Flow Chart			
Evaluation	Inclusion	Retrospective Eligibility Period: At CAD diagnosis between January 1st, 2009 – January 1st, 2019 (index date)	Retrospective Patient Follow-up: From the index date until study end (January 1st, 2020) or patient death or lost to follow-up, whichever occurs first
Informed consent form	Date of next routine consultation at the site (Italy only, for patients to sign the ICF at site as per local regulation)	Signature of the ICF prior to data collection	
Inclusion criteria	
 
Adult patients aged ≥18 years
 
Patients who fully meet the diagnostic criteria (see opposite)
 
Evidence of a signed and dated informed consent document indicating that the patient (or a legally acceptable representative) has been informed of all pertinent aspects of the study
 
	After they agree signing the informed consent form, adult patients aged ≥18 years diagnosed between January 1 st , 2009 and January 1 st , 2019 with an explicit cold AIHA (CAD) based on: 
 
Presence of chronic hemolysis
 
 AND 
 
A positive direct antiglobulin test (DAT), with a typical DAT pattern of a positive monospecific test for C3d only
 
OR
 
A positive direct antiglobulin test (DAT), with a typical DAT pattern of a weakly positive for IgG in addition to C3d
 
	
Exclusion criteria	N/A	
 
Patient with any other form of hemolytic anemia, including CAS and mixed AIHA
 
Presence of records of any cause of secondary CAS, [e.g. a concurrent diagnosis of any type of lymphoma, multiple myelomas, chronic lymphocytic leukemia, Waldenström macroglobulinemia, other active cancer, or recent infection with mycoplasma pneumoniae, Epstein-Barr virus, cytomegalovirus; autoimmune diseases (SLE)]
 
	
Patient demographics	Date of birth (month, year); Sex	N/A	N/A
Relevant medical history	N/A	
 
Any chronic or serious disease other than CAD and diagnostic date
 
Risk factors for TE
 
Medical history of TE
 
	N/A
CAD characteristics	N/A	
 
Age at onset of anemia or clinical symptoms
 
Age at diagnosis
 
Clinical presentation at or before diagnosis
 
Biological features at diagnosis
 
Transfusion history
 
	
 
Disease status over follow-up
 
History of hemolytic exacerbation/flares
 

Thromboembolic events	N/A	
 
Type of TE events (arterial and venous) and other events and dates
 
Situational circumstances in the weeks prior to a TE
 
	

Property of the Sanofi-Aventis Groupe - strictly confidential

Protocol template for disease observational studies			
		Research and Development	
QSD-003149	Disease observational study with disease Application Date (DD/MM/YYYY) : dd-Mmm-yy protoco v. 6.0 yyy	09/11/2020	EFFECTIVE

<DD-MM-YYYY HH:mm:ss> < 15-01-2021 21:03:21 > UTC \_\_\_\_

**Formatted:** Left, Tab stops: 8,89 cm, Centered + 17,1 cm, Right

Study Number: GER-CAD-19-11180

Version number: ~~V6~~V7.0

primary data collection

Drug therapy associated with CAD	N/A	
 
• Agent/s (including any Corticosteroid Containing Therapy and Rituximab)
 
• Daily dose for corticosteroids
 
• Duration of therapy, line of treatment
 
• Treatment response (complete response, partial response, non-response)
 
• Splenectomy
 
• Thromboprophylaxis
 

Direct HCRU associated with TE	N/A	
 
• All-cause inpatient admissions and length of stay (LOS)
 
• Outpatient visits
 
• Admissions to ICU and LOS
 
• Emergency room (ER) visits
 
• Surgical and other major procedures
 

Patient vital status	N/A	
 
• Date of death
 
• Cause of death
 

AIHA: autoimmune hemolytic anemia; CAD: Cold Agglutinin Disease; CAS: Cold Agglutinin Syndrome; DAT: Direct Antiglobulin Test; DVT: Deep Venous Thrombosis; ER: Emergency room; ICF: Informed Consent Form; ICU: Intensive Care Unit; IgG: Immunoglobulin G; LOS: length of stay; N/A: Not Applicable; PE: Pulmonary Embolism

Protocol template for disease observational studies				
			Research and Development	
QSD-003149	Disease observational study protocol v. 6.0yyyy	with disease	Application Date (DD/MM/YYYY) : dd-Mmm- 09/11/2020	EFFECTIVE

<DD-MM-YYYY HH:mm:ss> < 15-01-2021 21:03:21 > UTC

primary data collection  
Study Number: GER-CAD-19-11180

Version number: ~~V6~~V7.0

#### 4 LIST OF ABBREVIATIONS

AIHA	AutoImmune Hemolytic Anemia
CAD	Cold Agglutinin Disease
CAS	Cold Agglutinin Syndrome
CVC	Cardio-Vascular Condition
DAT	Direct Antiglobulin Test
DVT	Deep Venous Thrombosis
EC	Ethics Committee
ER	Emergency room
HCRU	Health Care Resource Utilization
ICF	Informed Consent Form
ICU	Intensive Care Unit
IgG	Immunoglobulin G
LDH	Lactate DeHydrogenase
LOS	Length Of Stay
N/A	Not Applicable
PE	Pulmonary Embolism
PPPM	Per Patient Per Month
SLE	Systemic Lupus Erythematosus
TE	Thromboembolic event
VTE	Venous ThromboEmbolism.

Property of the Sanofi-Aventis Groupe - strictly confidential

Protocol template for disease observational studies					
				Research and Development	
QSD-003149	Disease observational study	with disease	Application Date (DD/MM/YYYY) : dd-Mmm-09/11/2020	EFFECTIVE	
protoco v. 6.0		yyyy	<del><DD-MM-YYYY HH:mm:ss> <15-01-2021 21:03:21 > UTC</del>		

Formatted: Left, Tab stops: 8,89 cm, Centered + 17,1 cm, Right

primary data collection  
Study Number: GER-CAD-19-11180

Version number: ~~V6~~V7.0

## 5 INTRODUCTION AND RATIONALE

### 5.1 INTRODUCTION

Cold agglutinin-mediated autoimmune haemolytic anaemia (cold agglutinin-mediated AIHA) is a complement-mediated haemolytic disorder in which clonal or oligoclonal IgM antibody binds to red blood cell (RBC) antigens in sites of the body where the temperature is low (i.e. cold agglutinins). This leads to RBC agglutination and activation of the classical complement pathway and extravascular hemolysis (1, 2). Cold agglutinin-mediated AIHA can occur in the setting of an underlying viral infection, lymphoid malignancy or autoimmune disorders such as systemic sclerosis (scleroderma) and rheumatoid arthritis (3, 4), and is then referred to as secondary cold-agglutinin syndrome (CAS). Most cases arise without one of these underlying disorders and are thought to originate from a low-grade lymphoproliferative disorder. They are referred to as cold agglutinin disease (CAD)

The prevalence of CAD is estimated to be 16.2 cases per million, with an incidence rate of 1.0 case per million person-years; these estimates may be several fold higher in colder climates (5). Studies have demonstrated a slightly higher prevalence in females and a mean age at presentation in the mid to late 60s, with a broad range (30s to 90s) (5-7).

Most common clinical manifestations include cold-induced symptoms (mostly acrocyanosis), usually present in 52 % of patients, or up to 90% in colder climates such as in Scandinavia (5, 7). Ninety per cent of cases present anaemia (median haemoglobin, 9.5 g/dL, with some individuals in the normal range and others as low as 4.5 g/dL) (5-7). Symptoms attributable to anaemia include fatigue, shortness of breath, asthenia, angina and dyspnoea, which can be associated with substantial impairment in quality of life. Ninety per cent of cases present markers of haemolysis (high lactate dehydrogenase [LDH] and bilirubin, low haptoglobin). The severity of haemolysis can range from compensated haemolysis without anaemia to severe haemolytic anaemia requiring transfusion (5, 7). Spontaneous exacerbations and remissions in the course of the disease are to be expected, e.g. some individuals may have chronic compensated haemolytic anaemia with episodes of more severe anaemia due to increased haemolysis precipitated by cold temperatures or by febrile or other acute illnesses (e.g. episodes of the common cold, pneumonia). Therefore, patient needs for RBC transfusions fluctuate over time according to the occurrence of severe anaemia and individuals with mild disease may only require transfusions in the setting of severe haemolysis precipitated by infection or during the winter months (5, 8). Overall, the extent of

Protocol template for disease observational studies				
			Research and Development	
QSD-003149	Disease observational study protocol v. 6.0	with disease	Application Date (DD/MM/YYYY) : dd-Mmm- 09/11/2020	EFFECTIVE

<DD-MM-YYYY HH:mm:ss> < 15-01-2021 21:03:21 > UTC

primary data collection  
Study Number: GER-CAD-19-11180

Version number: ~~V6~~V7.0

CAD subjects utilizing RBC transfusions, either preceding diagnosis or during follow-up ranges from 40% to 100% (5).

While twenty four percent of patients are treated with supportive/symptomatic care alone (5), the remaining 76 % receive off-label CAD-directed medical therapy to reduce antibody production and maintain an acceptable haemoglobin levels (9, 10). Therapy generally involves rituximab in combination or as monotherapy, or bortezomib for individuals for whom a rituximab-containing regimen is ineffective or contraindicated (9). Randomized trials to assess the efficacy of rituximab in CAD have not been performed, but case series have reported response rates of more than 50 percent; many of the responses are partial (complete responses observed in only 21% of CAD patients) and with a slow response time (11, 12). Many patients continue to relapse despite the use of multiple lines of therapy, the median duration of response ranging from 6.5 to 11 months (11, 13).

Overall, the prognosis of CAD patients depends on the severity of the disease, with a median overall survival of 10.6 to 12.5 years from disease onset (5-7). Mortality in CAD patients has been reported to be significantly increased compared with a general population matched cohort (19). Causes of death include severe anaemia complications, ischemic stroke, and infection. However, information on mortality is limited, with most of the CAD-related literature being composed of case reports and small case series, and several methodological issues should be considered when interpreting existing data for larger cohorts.

#### CAD and risk of thromboembolic events (TEs)

Recent data suggest a correlation between CAD and thromboembolic events (TEs), which can impact quality of life and also lead to premature mortality (14, 15). TEs can also substantially increase disease burden and cost of treatment in CAD; in the general population, ten to thirty percent of patients die within 1 month of diagnosis of a venous thrombotic event (VTE), and among those who survive, 50% have long-term complications (16). An incident VTE has been estimated to cost between \$12 000 and \$15 000 in 2014 in the USA, which increased to \$18 000-\$23 000 when including subsequent complications (17).

Nevertheless, TE data in CAD is sparse, and the rarity of CAD limits the ability to perform large population-based studies. Several methodological limitations should be considered when interpreting existing TE data from the largest population-based studies in CAD and TE; a retrospective study in the USA involving a cohort of 608 individuals diagnosed with CAD from an insurance-based registry and nearly 6,000 matched controls recorded (venous and arterial) TE

Property of the Sanofi-Aventis Groupe - strictly confidential

Protocol template for disease observational studies					
				Research and Development	
QSD-003149	Disease observational study	with disease	Application Date (DD/MM/YYYY) : dd-Mmm- 09/11/2020	EFFECTIVE	

<DD-MM-YYYY HH:mm:ss> < 15-01-2021 21:03:21 > UTC

Formatted: Left, Tab stops: 8,89 cm, Centered + 17,1 cm, Right

primary data collection  
Study Number: GER-CAD-19-11180

Version number: ~~V6~~V7.0

during a 10-year period in 30 percent of those with CAD versus 18 percent of controls (adjusted hazard ratio [HR], 1.94; 95% confidence interval [CI], 1.64-2.30) (18), but misclassification due to coding errors inherent to claims data is likely. A smaller study from a Danish registry found an increased rate of TE in CAD patients as compared with age- and sex-matched controls (19), but there were also some methodology issues associated with the lack of validation of diagnostic codes in such registry.

## 5.2 RATIONALE

Therapies that target the classical complement pathway components responsible for extravascular hemolysis in CAD are under investigation. Sutimlimab is a humanized monoclonal antibody that targets C1s and has the potential to reduce extravascular hemolysis mediated by C3b (1, 20-23). Its efficacy was demonstrated in a small series of 10 patients with primary CAD and ongoing hemolytic anemia (24). An extension study in which sutimlimab was given as maintenance therapy demonstrated sustained improvements in hemoglobin and suppression of hemolysis (25).

In the context of the coming introduction of sutimlimab and other new therapies in Germany, Italy and Austria, it is important to collect up-to-date and comprehensive data on the burden of CAD on patients and the health care system in these countries. Due to the limited data from longitudinal studies on the incidence of TE, TE-related mortality, risk factors and impact on healthcare resource utilisation (HCRU) in CAD patients, this study will analyse TE incidence and mortality as documented in CAD patient medical records in the countries of interest. Results will be used to inform the future local HTA dossier submissions for sutimlimab across the European region. This information will also be important to achieve greater awareness among health care providers about the burden of this disease and inform about CAD patients who might be at risk of TEs and mortality. This data, which will be made publicly available, may ultimately help to promote implementation of appropriate prevention strategies, diagnosis of TE, and patient management.

Protocol template for disease observational studies				
			Research and Development	
QSD-003149	Disease observational study	with disease	Application Date (DD/MM/YYYY) : dd-Mmm-09/11/2020	EFFECTIVE

<DD-MM-YYYY HH:mm:ss> < 15-01-2021 21:03:21 > UTC

primary data collection  
Study Number: GER-CAD-19-11180

Version number: ~~V6~~V7.0

## 6 STUDY OBJECTIVES AND OUTCOMES

The study objectives are to better understand thrombotic events (TEs) and mortality in CAD:

### Primary objective

- To estimate incidence rates of thrombotic events (TE) in CAD

### Secondary objective(s)

- To characterize TEs in CAD and the risk factors for developing TE in CAD
- To estimate mortality rates in CAD, all-cause, and by underlying cause
- To characterize health care resource utilization (HCRU) associated with TEs in CAD.

**Table 1 - Objectives and outcomes**

Objectives	Outcomes
Primary	

 
To estimate incidence rates of thrombotic events (TEs) in CAD
 
	
 
Crude incidence rate of TE (overall and by type)
 

Secondary	

 
To characterize TEs in CAD and the risk factors for developing TE in CAD
 
To estimate mortality rates in CAD, all-cause, and by underlying cause
 
To assess health care resource utilization (HCRU) associated with TEs in CAD
 
	
 
Analysis of thromboembolic complications in patients with CAD: 
 
Incidence rate of TE by type (arterial, venous) after CAD diagnosis
 
Cumulative incidence of TE after CAD diagnosis
 
Correlation between CAD-clinical severity and TE occurrence
 
 
 
OS (Overall Survival) in CAD / mortality rate: 
 
Mortality rate in CAD, all cause and cause-specific mortality
 
Overall survival
 
 
 
Direct HCRU associated with TE in CAD: 
 
Percentage of patients with TE-related inpatient hospitalizations, ER, ICU and outpatient visits
 
Length of stay of inpatient hospitalizations related to TEs
 
Number of procedures / surgeries associated with TE diagnosis and management
 
 
 

Property of the Sanofi-Aventis Groupe - strictly confidential

Protocol template for disease observational studies				
			Research and Development	
QSD-003149	Disease observational study protocol v. 6.0	with disease	Application Date (DD/MM/YYYY) : dd-Mmm- 09/11/2020	EFFECTIVE

<DD-MM-YYYY HH:mm:ss> < 15-01-2021 21:03:21 > UTC

Formatted: Left, Tab stops: 8,89 cm, Centered + 17,1 cm, Right

primary data collection  
Study Number: GER-CAD-19-11180

Version number: ~~V6~~V7.0

## 7 STUDY DESIGN

Operational criteria for CAD definition are as follows:

An explicit cold AIHA (CAD) diagnosis in the patient medical chart between January 1st, 2009 and January 1st, 2019, based on:

- Presence of chronic hemolysis
- A positive direct antiglobulin test (DAT), with a typical DAT pattern of a positive monospecific test for C3d only  
OR  
A positive direct antiglobulin test (DAT), with a typical DAT pattern of a weakly positive for IgG in addition to C3d
- Absence of records of any cause of secondary CAS, [e.g. a concurrent diagnosis of any type of lymphoma, multiple myeloma, chronic lymphocytic leukemia, Waldenström macroglobulinemia, other active cancer, or recent infection with mycoplasma pneumoniae, Epstein-Barr virus, cytomegalovirus, autoimmune disorders (SLE)]

However, as this study will be conducted in a real-world setting with treating physicians assessing CAD vs CAS, reported patients who were diagnosed with CAD but whose medical records do not capture the data required to define CAD using strict haemato-immunologic diagnosis criteria (High titer cold reactive antibody (CA) (most often defined as  $\geq 64$  at 4°C); CA with a thermal amplitude  $<30^{\circ}\text{C}$ ), will be included in the study and classified as “presumed CAD”.

### 7.1 DESCRIPTION OF THE STUDY DESIGN

This is a European, multicenter, observational study of all adult patients with a CAD diagnosis from January 1st, 2009 through January 1st, 2019 seen at hematology/oncology centers in Germany, Italy and Austria.

Protocol template for disease observational studies				
			Research and Development	
QSD-003149	Disease observational study	with disease	Application Date (DD/MM/YYYY) : dd-Mmm-	EFFECTIVE
	protoco v. 6.0	yyyy	09/11/2020	

<DD-MM-YYYY HH:mm:ss> < 15-01-2021 21:03:21 > UTC

primary data collection  
Study Number: GER-CAD-19-11180

Version number: ~~V6~~V7.0

This observational study plans to collect information on the thromboembolic risk and mortality in CAD patients. Data will be extracted retrospectively from the initial date of CAD diagnosis until the earliest of death, end of data availability (*i.e.* lost to follow-up) or end of data collection set on January 1st, 2020 for approximately 170 patients in total. The design of the study will mirror real life management of these patients.

Pseudo-anonymous subject-level data will be transcribed, retrospectively, from medical records onto electronic case report forms (eCRFs) by study investigators routinely involved in the management of these patients (or delegates at the study site). No examinations or procedures apart from those occurring as part of the patient's routine clinical care are required for this study.

Chart reviews will be performed regardless of whether patients are alive at the time of data collection. In order to include the maximum follow-up data available per patient, patient's medical records will be abstracted retrospectively from initial clinical manifestation of CAD until death, loss to follow-up or end of data collection, whichever comes first. There will be no prospective follow-up period.

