	
immunologic diagnosis criteria [ie High titer cold reactive antibody (CA) (most often defined as <math>\geq 64</math> at 4°C); CA with a thermal amplitude <30°C] will be included in the study and classified as "presumed CAD".
 
Exclusion Criteria
 
 
• Patient with any other form of hemolytic anemia, including CAS and mixed AIHA
 
• Presence of records of any cause of secondary CAS at diagnosis [concurrent diagnosis of any type of lymphoma, multiple myeloma, chronic lymphocytic leukemia, Waldenström macroglobulinemia, other active cancer, or recent infection with mycoplasma pneumoniae Epstein-Barr virus, cytomegalovirus, Autoimmune disorders (SLE)]
 
 
Expected number of patients: Approx. 170

RECRUITMENT MODALITIES	
Selection of sites/investigators
 
A feasibility study will be run to select study sites/investigators able to reach recruitment goals and having the infrastructure or material resources necessary for completing the chart review study. A comprehensive list of hematology and oncology hospitals potentially managing CAD patients will be approached for the feasibility study in Germany. Referral centers of CAD expertise will be contacted in Italy and Austria.
 
Selection of patients
 
Study investigators routinely involved in the management of CAD patients (or delegates at the study site) will screen medical records of their patients diagnosed with CAD between January 1st, 2009 and January 1st, 2019 in a consecutive, retrospective order and include all those who fulfil pre-defined study eligibility criteria.

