#### 8.4 MODALITIES OF RECRUITMENT

Primary medical records will be available for review from specialty clinics treating CAD patients who agreed to participate in the patient chart review following a feasibility study.

Using the online screening form, study investigators routinely involved in the management of CAD patients (or delegates at the study site) will screen medical records of their patients diagnosed with CAD between January 1st, 2009 and January 1st, 2019 in a consecutive, retrospective order and include all those who fulfil pre-defined study eligibility criteria. Patient selection will be based on systematic sampling, *i.e.* all consecutive eligible patients are expected to be included in the study. Target sample size will be approximately 170 charts.

Property of the Sanofi-Aventis Groupe - strictly confidential

Protocol template for disease observational studies				
			Research and Development	
QSD-003149	Disease observational study protocol v. 6.0	with disease	Application Date (DD/MM/YYYY) :dd-Mmm- 09/11/2020	EFFECTIVE

<DD-MM-YYYY HH:mm:ss> <15-01-2021 21:03:21 > UTC

Formatted: Left, Tab stops: 8,89 cm, Centered + 17,1 cm, Right

primary data collection  
Study Number: GER-CAD-19-11180

Version number: ~~V6~~V7.0

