## 9 SELECTION OF INVESTIGATORS

A list of sites managing CAD patients in each participating country will be designed by Cerner Enviza and the Sponsor based on data availability and characteristics of the health care system of each study country. In Germany, a comprehensive list of hematology and oncology hospitals potentially managing CAD patients across the country will be created from several sources, including Orphanet and PubMed. In Italy and Austria, a list of referral centers managing CAD patients based on existing input from pre-marketing clinical studies, local affiliates of the Sponsor and external advisors will be used for site selection.

A feasibility study will be run to select study sites from such lists. A site qualification questionnaire tailored to the study and country will be designed to evaluate feasibility and verification of the capability and willingness of the potential sites to complete the study. During the feasibility stage, research assistants will contact physicians from each site for completion of the site qualification questionnaire over the phone or via email to determine both site and physician eligibility to participate in the study. If a physician does not qualify for the study or refuses to participate in the study, he/she may refer another physician in the same hospital. If he/she qualifies but refuses to participate, the reasons for non-participation will be reported.

Within each country, the target number of centers participating in the study will be determined based on the capacity of each participating center to access patients meeting the eligibility criteria, as assessed by the feasibility study. Target number of centers may be adjusted accordingly.

Investigator selection will be performed independently in each country based on the feasibility assessment and eligibility criteria listed below.

Investigators may be hematologists, onco-hematologists or any other specialists involved in the management of adult CAD patients. Their eligibility will be based on the following criteria:

- Physicians working in centers managing patients with CAD and having available the appropriate facilities or equipment to perform research.
- Personally managing CAD patients
- Assessing or managing the thromboembolic risk in their CAD patients, or being informed by colleagues when their CAD patients present with a thromboembolic risk
- Agreeing to comply with the study protocol and data collection procedures.

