## 10 DATA COLLECTION

### 10.1 DATA COLLECTION SCHEDULE

Pseudo-anonymized epidemiologic, clinical, and biologic data from patient's medical charts will be extracted by site staff from the initial date of CAD diagnosis until the earliest of death, end of data availability (*i.e.* lost to follow-up) or end of data collection set on January 1st, 2020. Diagnosis must have occurred between January 1st, 2009 and January 1st, 2019. Duration of follow-up will depend on time of diagnosis; a priori, enrolled patients diagnosed earlier during this time period will have a longer follow-up period than those diagnosed later. There will be no minimum duration of follow-up. However, HCRU analysis will require having data from patient medical records available for a minimum of time following a TE to ensure all costs associated with each TE are covered. Per-patient-per-month (PPPM) HCRU will be calculated during the variable follow-up period of up to 12 months after the TE diagnosis.

There will be no prospective follow-up period. No examinations or procedures apart from those occurring as part of the patient's routine clinical care are required for this study.

The schedule of events is described in Table 2: Schedule of Recommended Study Assessments

Since this study is retrospective in nature, results will be collected as available.

Table 2: Schedule of Recommended Study Assessments

Data to be collected	Assessments	Screening	Baseline	Follow-up
Eligibility criteria		X		
Written informed consent (IC)		X		
Demographics			X	
Medical History	Comorbidities; TE risk factors		X	X
CAD diagnosis history and disease status	Clinical findings; indicators of anemia and hemolysis		X	X

Property of the Sanofi-Aventis Groupe - strictly confidential

Protocol template for disease observational studies					
				Research and Development	
QSD-003149	Disease observational study	with disease	Application Date (DD/MM/YYYY) : dd-Mmm-09/11/2020	EFFECTIVE	

<DD-MM-YYYY HH:mm:ss> < 15-01-2021 21:03:21 > UTC

Formatted: Left, Tab stops: 8,89 cm, Centered + 17,1 cm, Right

primary data collection  
Study Number: GER-CAD-19-11180

Version number: ~~V6~~V7.0

Significant medical events	TE dates and types; previous history of TE		X	X
Relevant treatment history	CAD-specific treatment patterns; response to treatment		X	X
Direct HCRU related to TE	Hospitalizations and length of stay; outpatient, ER and ICU visits			X
Patient vital status	Cause of death; date of death			X

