### 13.4 STATISTICAL METHODS

This study is primarily descriptive in nature and does not include formal statistical hypothesis testing. A formal statistical analysis plan (SAP) that will provide details of all analyses and presentation of study data will be approved prior to database lock. All final analyses will be performed once the data from all patients has been collected in the database, cleaned and database lock has occurred.

All variables will be summarized descriptively through tabular displays of mean, median, ranges and standard deviations (SD) of continuous variables and frequency distributions of categorical variables. Changes in disease activity closest to the date of each study event will be described, where data are available. Crude incidence rates (with 95% CI) will be calculated from the number of TE after CAD diagnosis and the sum of individual person-years contributed by the CAD population during the study period. The mortality rate will also be estimated in this way. For event analysis, the main events evaluated will include time to first TE and time to death. The cumulative incidence of TE will be estimated using Kaplan-Meier survival analysis accounting for mortality as a competing risk event if sample size allows it. Descriptive analysis will be used to identify risk factors associated with occurrence of TE.

Protocol template for disease observational studies				
			Research and Development	
QSD-003149	Disease observational study	with disease	Application Date (DD/MM/YYYY) : dd-Mmm-09/11/2020	EFFECTIVE

<DD-MM-YYYY HH:mm:ss> < 15-01-2021 21:03:21 > UTC

primary data collection  
Study Number: GER-CAD-19-11180

Version number: ~~V6~~V7.0

Due to the potentially variable length of follow-up, HCRU will be calculated as per-patient-per-month (PPPM) during the variable follow-up period of up to 12 months after the TE diagnosis. Patients with both “confirmed” and “presumed” CAD will be included in the primary analysis. Sensitivity analysis will be performed to address any potential misclassification in CAD diagnosis; patients who fully meet the inclusion criteria will be classified as having “confirmed CAD”; reported patients who were diagnosed with CAD but whose medical records do not capture all the data required to define CAD or distinguish CAD vs CAS using strict haemato-immunologic diagnosis criteria will be classified as “presumed CAD”.

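### Follow-up starts at CAD diagnosis although patients enter only on reaching a participating centre, so time before a late referral biases the mortality rate down and overall survival up

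*Protocol*

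**What the plan says.** **Time zero.** The flow chart in Section 2.2 makes CAD diagnosis the index date and follows patients "From the index date until study end", death or loss to follow-up. Section 7.1 has "Data will be extracted retrospectively from the initial date of CAD diagnosis until the earliest of death, end of data availability". Section 10.1 adds "Duration of follow-up will depend on time of diagnosis" and sets no minimum duration.

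**Rates.** Section 13.4 divides TEs after diagnosis by "the sum of individual person-years contributed by the CAD population during the study period" and computes the mortality rate in the same way. Mortality and overall survival are secondary outcomes (Section 6, Table 1).

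**Route of entry.** Section 7.1 describes patients "seen at hematology/oncology centers in Germany, Italy and Austria". Under Section 8.4 investigators "will screen medical records of their patients diagnosed with CAD". The synopsis states "Referral centers of CAD expertise will be contacted in Italy and Austria", and Section 9 refers to "In Italy and Austria, a list of referral centers managing CAD patients based on existing input from pre-marketing clinical studies". For Germany, Section 9 uses a comprehensive hospital list. Neither Section 8.2 nor 8.3 requires diagnosis at the centre or a first visit close to diagnosis.

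**What is not there.** The date of first visit or referral is not among the variables in Section 10.3.1, a list that is expressly not exhaustive, nor in Table 2. The only admitted reason for under-estimated mortality, at the end of Section 10.3.1, is deaths that go unrecorded.

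**An inconsistency nearby.** The synopsis begins the analysed record at the first relevant examination, while Section 7.1 names both diagnosis and first clinical manifestation as the start of abstraction. The index date in Section 2.2 and the rate definition in Section 13.4 still point to diagnosis as time zero.

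**The concern.** A chart review finds only people who have a chart. Someone diagnosed at another hospital who died before reaching a participating centre leaves no record there. Someone with the same diagnosis date who lived long enough to be referred is included, and is credited with all the time since diagnosis. This is left truncation treated as complete observation.

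Deceased patients are eligible and sampling is consecutive, but neither repairs this: both apply only to people who reached the centre. A larger sample would not help either.

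Section 5.2 intends the results for HTA dossiers on disease burden. A mortality rate that is too low, or a survival curve that is too favourable, would go straight into those submissions, and no variable listed in the protocol would let a reader judge the size of the error.

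**Working it through.** **1. The plan's own figure.** Section 13.1 gives margins of 6.0% and 6.9% for TE proportions of 20% and 30% with n = 170. These reproduce: 1.96 × √(0.20 × 0.80 / 170) = 6.01% and 1.96 × √(0.30 × 0.70 / 170) = 6.89%. They concern a proportion, do not involve person-time, and are not in dispute.

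**2. The bias in one line.** Among included patients let d be deaths, T_obs the person-years from first visit onward, and T_pre the person-years between diagnosis and first visit. All d deaths fall in T_obs. With f = T_pre / (T_obs + T_pre),

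planned rate = d / (T_obs + T_pre) = (d / T_obs) × (1 − f).

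The planned mortality rate thus falls short of the rate over time actually under observation by exactly the fraction f.

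**3. Inputs for an illustration.**
- From the protocol: diagnosis from 1 January 2009 to 1 January 2019 and end of follow-up on 1 January 2020, hence 1-11 years of potential follow-up (taken as uniform); 170 patients; median survival 10.6-12.5 years (Section 5.1, from disease onset, here treated as from diagnosis). Exponential hazard = ln 2 / 10.6 = 0.0654 and ln 2 / 12.5 = 0.0555 per year.
- Assumed: 20% or 40% referred after diagnosis, with exponential delay of mean 1, 2 or 3 years, unrelated to risk.
- A simulated patient is included only if alive at first visit and if that visit precedes the end of follow-up.

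**4. Mortality results** (3 million simulated patients, scaled to 170; paired entries are for medians of 10.6 / 12.5 years):

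| Referred late | Mean delay | f | Planned ÷ true rate | Deaths | Person-years |
|---|---|---|---|---|---|
| 20% | 1 y | 3.3% / 3.3% | 0.97 / 0.97 | 52.0 / 45.6 | 823 / 850 |
| 20% | 2 y | 5.0% / 4.9% | 0.95 / 0.95 | 51.7 / 45.2 | 832 / 858 |
| 20% | 3 y | 5.6% / 5.6% | 0.94 / 0.94 | 51.6 / 45.1 | 835 / 862 |
| 40% | 1 y | 6.7% / 6.6% | 0.93 / 0.93 | 50.9 / 44.5 | 835 / 860 |
| 40% | 2 y | 10.1% / 10.0% | 0.90 / 0.90 | 50.1 / 43.8 | 853 / 878 |
| 40% | 3 y | 11.6% / 11.6% | 0.88 / 0.88 | 49.8 / 43.5 | 862 / 887 |

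Last row, median 12.5 years: 43.5 / 887 = 0.0490, against a true 0.0555. Removing the immortal time, 11.6% × 887 = 103 person-years, gives 43.5 / 784 = 0.0555. Delayed entry returns a ratio of 1.00 in every row.

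With wider assumptions (25-75% referred late, mean delay 0.5-3 years, and TEs that can be fatal) the shortfall runs from about 2% to 23%.

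**5. Against sampling error.** With 52 deaths the relative 95% half-width is about 1.96 / √52 = 27%; with 43 deaths, 1.96 / √43 = 30%.

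**6. TE rates.** The TE hazard is taken from the 30% over 10 years quoted in Section 5.1: −ln(0.70) / 10 = 0.036 per year. TE case fatality is 0-30% (assumed; Section 5.1 quotes 10-30% for venous events in the general population), and median survival is 12.5 years. Scenarios run from 50% referred with mean delay 1 year to 75% with 3 years.
- No pre-referral TE in the centre's chart: about 10% to 28% too low.
- Half of them found: about 5% to 17% too low.
- All found: 0% to 7% too low, because only fatal TEs are lost.
- All found, none fatal, but half of the late group referred because a TE occurred (a separate assumption): 10-22% too high.

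**The case against.** The strongest reply is that late referral is inferred. The protocol nowhere says that patients were diagnosed elsewhere, and Section 8.1 can be read as screening patients diagnosed at each site. Referral centres are named only for Italy and Austria. This stands as a limit on size: patients diagnosed at the centre are unaffected, and Germany may be affected less. It does not remove the problem, because no criterion restricts entry to patients diagnosed on site.

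A second reply is that the variable list is open and the statistical analysis plan could add delayed entry. That is true, and the missing date alone would be no finding. But the protocol itself fixes the index date and the rate definition, and delayed entry is possible only if the date is collected.

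A third reply is that a 3-12% bias is well inside an interval of ±27-30%. It is, but the interval does not cover systematic error.

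Two stronger readings are tempting. A reader might infer that the rule also dilutes the primary TE rate. The documents do not support a fixed direction: TE dates and TE history are collected, so non-fatal pre-referral events may be in the chart, and referral prompted by a TE pushes the rate up. A reader might also infer that the extra date removes the bias entirely. In the table it does so because referral was simulated as unrelated to risk. If half the patients carry four times the hazard of the rest and are referred sooner (mean delay 1 versus 4 years, assumed), the planned rate is 3-6% low and delayed entry overshoots by 2-4%.

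**Conclusion.** The concern holds for the mortality rate and overall survival. Starting the clock at diagnosis counts as observed follow-up a period in which no included patient can die. This biases the mortality rate downward and survival upward as soon as any patient is referred after diagnosis. Under the assumed 20-40% late referral and mean delay of 1-3 years, the mortality rate is about 3-12% too low. The true share and delay cannot be read from the protocol. The bias is smaller than the sampling error with about 43-52 deaths, but it does not shrink with more patients.

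For TE rates only a conditional statement is justified: fatal and unrecorded pre-referral events lower the rate, and referral triggered by a TE raises it. The point merits a change to the plan, but it does not invalidate the primary outcome.

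**What to change.** Add the date of first visit at the participating centre to Section 10.3.1 and the eCRF. In Section 13.4:
- Estimate the mortality rate and overall survival with delayed entry, so that person-time and risk sets begin at the later of CAD diagnosis and first visit. Show the from-diagnosis analysis alongside.
- For TE rates and cumulative incidence, give the delayed-entry version as a sensitivity analysis and report TEs between diagnosis and first visit separately.
- State that delayed entry removes the bias fully only if referral timing is unrelated to risk.
- Use one definition of the start of follow-up in the synopsis and Section 7.1.

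The cost is one added field, including for charts already completed: the first site was to be active on 29 August 2022, version 7.0 is dated 27 July 2023, and last data in is October 2023. The field has to be filled before database lock, because the identification log for deceased, lost and non-visiting patients is then destroyed (Section 10.3.3). The analysis gives up about 3-12% of person-time under the assumptions above, and risk sets soon after diagnosis will be sparse.
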